Official Title:	Project ALTA: Advancing Long-term Improvements in Hypertension Outcomes through a Team-based Care Approach
NCT Number:	NCT03713515
Study Number:	18-01290
Document Type:	Study Protocol and Statistical Analysis Plan
Date of the Document:	
 December 22, 2025

CLINICAL STUDY PROTOCOL

Project ALTA: Advancing Long-term Improvements in Hypertension Outcomes through a Team-based Care Approach

Study Number

s18-01290

Sponsor

NIMHD

Protocol Version

December 19, 2025

version 13

Study Personnel

Principal Investigators

[name]
New York University
Email: [contact]

[name]
New York University
Email: [contact]

Investigator

[name]
New York University
Email: [contact]

Key Study Personnel:

[name]
New York University
Email: [contact]

Synopsis

Primary Objective

The primary objective of this study is to refine the practice facilitation (PF) strategies that will be tested in a cluster-randomized trial.

Secondary Objectives (if applicable)

1. To test the hypothesis that the refined PF strategy will result in a higher level of implementation fidelity of ALTA (primary outcome) and improved blood pressure (BP) control and antihypertensive medication adherence (secondary outcomes) at 12 months.
2. To explore potential moderating factors at the practice and individual levels (e.g., organizational capacity to change, evidence-based practice attitudes) that influence implementation of ALTA in a network of 10 safety-net primary care practices in New York.
3. To evaluate the impact of ALTA on the patient-provider relationship (i.e., relationship commitment, patient-provider trust, and patient anxiety in the interaction)
4. To determine whether changes in patient-provider relationship that result from ALTA are associated with changes in medication adherence and BP control (secondary outcomes)

Primary Outcome Variables

The primary outcome is the level of implementation fidelity of ALTA into routine care within the safety-net practices. Implementation fidelity is defined as the degree to which an intervention was delivered, as intended by program developers. We will use a mixed methods approach to assess the five core domains of implementation fidelity.

Secondary and Exploratory Outcome Variables (if applicable)

The secondary outcomes will be measures of clinical effectiveness—BP control and adherence to antihypertensive medications at the pre-intervention (baseline) and post-intervention (12 month) periods.

The tertiary outcomes will be measures of the patient-provider relationship – relationship commitment, patient-provider trust, and patient anxiety in the interaction– at the pre-intervention (baseline) and post-intervention (12 month) periods.

Study Duration

The study duration is 5 years. The pre-implementation phase will be 9 months and the implementation phase will be the remaining 4 years. Sites and participants enrolled in the

implementation phase will participate in the trial for 15 months. The approximate start date for the trial is September 1, 2018. The approximate end date is November 30, 2027.

Study Design

Using a mixed-methods design, the proposed study will be conducted in two phases: 1) A pre-implementation phase (surveys, QI interviews) and 2) an implementation phase.

For the pre-implementation phase, we will use a mixed methods observational research design to refine the PF strategies that will be tested in the implementation phase.

For the implementation phase, we will evaluate, in a stepped-wedge cluster randomized controlled trial, the effect of the PF strategy on the level of implementation fidelity (primary outcome) of ALTA, as well as on clinical outcomes (secondary outcomes) and the patient-provider relationship (tertiary outcomes) as compared to usual care at 12 months.

Study Population

The study population will include practice clinical and nonclinical staff and patients with uncontrolled hypertension (HTN) receiving care in the network of 10 safety-net primary care practices in New York.

Patient Eligibility Criteria

Inclusion Criteria:

- Be fluent in English or Spanish
- Be age 18 years or older
- Receiving care at one of the 10 safety-net primary care practices
- Have uncontrolled HTN documented in the electronic health record (EHR) on at least two visits in the past year (defined as an average BP \geq 140/90 mmHg)
- Have been prescribed at least one anti-hypertensive medication and be non-adherent to their medications, defined as adherence $<80\%$ in the preceding 12 months, as determined by prescription orders obtained from the clinic EHR.

Exclusion Criteria:

- Being deemed unable to comply with the study protocol (either self-selected or by indicating during screening that s/he could not complete all requested tasks)
- Participation in other hypertension-related clinical trials
- Have significant psychiatric comorbidity or reports of substance abuse (as documented in the EHR)
- Plan to discontinue care at the practice within the next 15 months

Clinic and nonclinical staff Eligibility Criteria

Inclusion criteria:

- Primary care provider (MD/DO, NP), Nurse, Medical Assistant, or administrative staff employed at the participating practices and interacts with at least five patients with a diagnosis of hypertension.

Exclusion criteria:

- Refuse to participate.

Number of Participants

Implementation Phase

Clinical and nonclinical staff:

Surveys and interviews: 204

Patients:

Surveys: Randomly selected sample of 70 patients from each of the 10 participating primary care clinics (n=700). We will also be selecting a sample of 300 patients across participating clinics who met the eligibility criteria but did not participate in ALTA to participate as a control group.

Interviews: A randomly selected subsample of 30 patients with uncontrolled HTN who participated in ALTA (n=700)

Table of Contents

1 – Introduction	9
1.1 Introductory Statement	9
2 – Background	10
2.1 Background/prevalence of research topic	10
3 – Rationale/Significance	11
3.1 Problem Statement	11
3.2 Purpose of Study/Potential Impact	11
3.3.1 Potential Benefits	12
3.3.2 Potential Risks	13
4 – Study Objectives	15
4.1 Hypothesis	15
4.2 Primary Objective	15
4.3 Secondary Objectives (if applicable)	15
5 – Study Design	16
5.1 General Design	16
5.1.1 Study Duration (if applicable)	17
5.1.2 Number of Study Sites	17
5.2.1 Primary Outcome Variables	17
5.2.2 Secondary and Exploratory Outcome Variables (if applicable)	17
5.3 Study Population	19
5.3.1 Number of Participants	19
5.3.2 Eligibility Criteria/Vulnerable Populations	20
6 – Methods	22
6.1 Description of PF implementation strategy	22
6.1.1 Usual Care (UC) Phase	22
6.1.2 Pre-implementation phase	22
6.1.3 Description of Implementation phase	23
6.1.4 Selection of Instruments/Outcome Measures	24
6.1.5 Intervention Administration	31
6.1.6 Reaction Management	32

6.2.1 Efficacy	32
6.2.2 Safety/Pregnancy-related policy	33
6.2.2.1 Adverse Events Definition and Reporting	33
6.2.3 Pharmacokinetics (if applicable)	33
6.2.4 Biomarkers (if applicable)	33
6.3.1 Study Schedule	33
6.3.2 Informed Consent	34

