5.1.1 Study Duration (if applicable)

The study duration is 24 months. During the UC phase, patients at the sites will receive standard HTN care delivered by their primary care providers for the first 3 months. The pre-implementation phase will be the following 6 months of the trial to refine the PF strategy that will be used during the implementation phase. The implementation phase will be 12 months and there will be two study visits: consent/baseline and 12-month follow-up.

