5.3.2 Eligibility Criteria/Vulnerable Populations

The study population will include practice clinical and nonclinical NYULH staff and patients with uncontrolled HTN receiving care in the network of 10 safety-net practices in New York.

Patient Eligibility Criteria

Inclusion Criteria:

- Be fluent in English or Spanish
- Be age 18 years or older
- Receiving care at one of the 10 practices
- Have uncontrolled HTN documented in the EHR on at least two visits in the past year (defined as an average BP \geq 140/90 mmHg)
- Have been prescribed at least one anti-hypertensive medication and be non-adherent to their medications, defined as adherence $<80\%$ in the preceding 12 months, as determined by prescription orders obtained from the clinic EHR.

Exclusion Criteria:

- Being deemed unable to comply with the study protocol (either self-selected or by indicating during screening that s/he could not complete all requested tasks)
- Participation in other hypertension-related clinical trials
- Have significant psychiatric comorbidity or reports of substance abuse (as documented in the EHR)
- Plan to discontinue care at the practice within the next 15 months

Clinic and nonclinical staff Eligibility Criteria

Inclusion criteria:

- Primary care provider (MD/DO, NP), Nurse, Medical Assistant, or administrative staff employed at the participating practices and interacts with at least five patients with a diagnosis of HTN.

Exclusion criteria:

- Refuse to participate.

Control group eligibility criteria

Inclusion criteria:

- Patients who fit the inclusion criteria of the intervention group

Exclusion criteria:

- The same exclusion criteria of the intervention group will be applied to the control group
- Patients who refuse to participate in the evaluation

As ALTA grows and becomes standard-of-care, we anticipate that some patients may crossover from the control group to intervention group. The opposite will not occur because that is considered a withdrawal from the study. Our sample size for the control group can remain dynamic in that fashion, and we will recruit until the end of the evaluation period.

Vulnerable Populations

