6.3.3 Screening

Trained RAs will be responsible for screening potentially eligible participants from the practices. Once a potentially eligible patient is identified for this study, they will be screened using a standardized form that outlines the study's inclusion and exclusion criteria. Study staff will obtain verbal consent prior to beginning the eligibility screening. Only participants that meet all eligibility criteria will provide written informed consent.

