6.3.4 Recruitment, Enrollment and Retention

Practice clinical and non-clinical staff will be recruited through study team attendance at the monthly staff meetings, email communications that describe the project including the overarching goals and what is expected of participants, and in-person or virtual meetings with the practices.

We will recruit approximately 500 patients across the practices who meet the following eligibility criteria (described above). Several strategies will be used to maximize the number

of eligible patient participants recruited per practice as described below. Signed informed consent will be obtained from participants who meet the study eligibility criteria.

Since this is a clinic wide initiative, we are broadening our eligibility criteria to include patients of all race and ethnicities, and not be exclusive to Latinx patients (this is also reflected in the change to our project name). We will still recruit a random sample of 70 patients per clinic that receive care in the 10 safety-net practices to participate in the surveys to assess our tertiary outcomes. Of this sample, 30 will be randomly selected to participate in an exit interview. Patients will be randomly selected from a list of patients who receive care in the clinics and have been exposed to the ALTA project. The same recruitment strategies will be employed to recruit 300 patients who receive care in the clinics and met eligibility for ALTA but did not ultimately participate in the project. All patients will provide written informed consent prior to participating in the study.

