6.3.6 End of Study and Follow Up

Patient Consent at baseline: During this visit, trained RAs will use a standardized form to screen patients based on the study's inclusion and exclusion criteria. Verbal consent will be obtained prior to beginning the eligibility screening. Only patients that meet all eligibility criteria will then complete the consent procedures, during which a trained RAs will describe the study in easy-to-understand language. If the patient remains interested, the RA will obtain written informed consent in the patient's preferred language (English or Spanish). The patient will then complete a demographic questionnaire, validated surveys on patient trust, relationship commitment and anxiety, and have their medical chart reviewed by a trained RA. This visit should take 15 minutes.

Final study visit at 12-Months (post randomization): At 12 months, trained RAs will repeat the chart review procedures for consenting patients, in accordance with IRB and

HIPAA regulations. Patients will also complete the same measures on patient trust, relationship commitment and anxiety. In addition, we will conduct semi-structured interviews with a random sample of 30 patients with uncontrolled HTN about their experiences with ALTA over the past 12 months and its impact on the patient-provider relationship, as well as recommendations for improvements. This visit will take approximately 60 minutes.

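### The two 12-month eligibility look-backs have no index date, so for survey patients sampled after ALTA exposure they can include months on ALTA and screen out patients who have improved

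*Combined protocol and SAP*

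**What the plan says.** Two criteria define the patient population, in the synopsis and again in section 5.3.2. The blood pressure criterion is "Have uncontrolled HTN documented in the electronic health record (EHR) on at least two visits in the past year", with an average of at least 140/90 mmHg. The adherence criterion is a level below 80% "in the preceding 12 months, as determined by prescription orders obtained from the clinic EHR". Neither place says from which date the year is counted back.

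On who is sampled, section 6.3.4 says: "Patients will be randomly selected from a list of patients who receive care in the clinics and have been exposed to the ALTA project". This gives 70 patients per clinic, 700 in all. On when the criteria are applied, section 6.3.3 says "Only participants that meet all eligibility criteria will provide written informed consent", and section 6.3.6 says that at the consent/baseline visit "trained RAs will use a standardized form to screen patients based on the" inclusion and exclusion criteria. Section 5.1.1 describes a 12-month implementation phase in which "there will be two study visits: consent/baseline and 12-month follow-up".

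The 300 controls are "Patients who fit the inclusion criteria of the intervention group". Section 6.3.4 adds that they were eligible for ALTA but did not take part.

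Section 6.1.1 points the other way. It has research assistants recruit eligible patients and collect baseline measures in the usual care phase, when ALTA is not running. The synopsis and section 5.2.2 also call baseline pre-intervention.

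**The concern.** A window counted back from screening, applied to someone already on ALTA, mixes months before and months under the intervention. Blood pressure and adherence are what ALTA is meant to change. A patient who has improved enough can therefore fail a criterion because of that improvement, while a patient who has not improved is more likely to stay eligible. Controls are screened with the same words but have no ALTA participation in their window, so the two groups can be selected on different bases.

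Three things are at stake in the consented sample: the relationship outcomes, the comparison of ALTA patients with controls, and tertiary objective 8 in section 4.4. That objective links change in the relationship to change in adherence and BP control, and losing improved patients narrows the range of the changes it has to work with.

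**Working it through.** The plan gives no figure on this point, so there is none to reproduce. The power statement in section 6.4.2 does not enter the argument.

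**1. When are patients recruited?** Recruitment in usual care (6.1.1) cannot describe a sample drawn from an exposed list (6.3.4), because nobody is exposed yet. It cannot describe the controls either: not having taken part (6.3.4), or having declined for the whole evaluation period (6.4.3.3), is known only after ALTA has been offered. Section 6.3.4 rebuilds the roster of potentially eligible patients monthly, and section 5.3.2 recruits controls to the end of the evaluation period. No section reconciles the two accounts or fixes eligibility at an earlier date.

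**2. Share of the window under ALTA.** With m months of ALTA before screening, the share is m/12: 0% at m = 0, 25% at 3, 50% at 6, 75% at 9 and 100% at 12. The documents do not give m.

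**3. When one patient stops qualifying.** Values here are assumed, with even spacing over the window.
- Proportion of days covered (PDC), b before and a under ALTA: m = 12(0.80 − b)/(a − b). From 0.70 to 0.90: 12 × 0.10/0.20 = 6.0 months. For b from 0.50 to 0.75 and a from 0.85 to 1.00, the range is 2.4 to 10.3 months.
- Mean systolic pressure, b before and a under ALTA: m = 12(b − 140)/(b − a). From 150 to 130: 12 × 10/20 = 6.0 months. For b from 145 to 160 and a from 125 to 135, the range is 3.0 to 9.6 months.

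**4. A population of such patients.** Assumptions: pre-ALTA mean systolic pressure normal (142, SD 14) and PDC normal (0.60, SD 0.18, clipped to 0–1), restricted to at least 140 mmHg and below 0.80; individual changes normal with SD 8 mmHg and 0.12; window value = pre-ALTA value + (m/12) × change; diastolic pressure and visit-to-visit variation ignored. The three scenarios are labelled by mean change. The last column is the mean systolic change among those kept in the middle scenario.

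| m | −5 mmHg, +0.05 | −8 mmHg, +0.10 | −12 mmHg, +0.15 | Change in those kept |
|---|---|---|---|---|
| 0 | 100% | 100% | 100% | −8.0 |
| 3 | 89% | 85% | 79% | −7.2 |
| 6 | 79% | 70% | 60% | −6.3 |
| 9 | 69% | 57% | 44% | −5.3 |
| 12 | 60% | 46% | 32% | −4.3 |

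The percentages are patients eligible before ALTA who still qualify at screening.

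**5. Sensitivity to when screening happens.** A second model assumes PDC uniform between 40% and 80%, systolic pressure 140 plus a gamma variable (mean 152), responders gaining 15–25 PDC points and losing 10–20 mmHg, and six evenly spaced readings. The share of responders screened out is:
- 35–58% if screening is spread evenly over 12 months of ALTA;
- 7–14% if it is spread over the first 3 months;
- about 2% if it falls in the first month.

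**6. Which analyses use these patients?** Section 6.1.4 takes secondary-outcome data from an EHR report on hypertension patients at the 10 practices. Section 6.4.2 powers BP control on 700 patients, section 6.3.6 repeats chart review at 12 months for consenting patients, and section 6.4.3.3 lists SBP, DBP and PDC among the tertiary outcomes. The analysis set for BP control and PDC is therefore not settled.

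**The case against.** The strongest reply is that patients are recruited before or at the start of ALTA. Section 6.1.1 says so. Two visits in a 12-month phase (5.1.1 and 6.3.1) fit best if consent is near its start. The 15 months of participation in the synopsis match 12 months plus the 3-month follow-up in section 5.1. Table 1 in section 3.2 also identifies uncontrolled, non-adherent patients from the registry before coaching, so eligibility might be meant to be settled there. This stands as a limit on size: with early screening the loss is small. It does not remove the point, because section 6.3.4 samples after exposure, sections 6.3.3 and 6.3.6 apply the criteria at screening, and nothing ends the window before ALTA.

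A second reply is that the blood pressure rule may need only two elevated visits. A responder with two high pre-ALTA readings in the window would then still qualify. In the second model, the loss with screening over 12 months falls to 27–41% of responders. That stands too, but the adherence criterion still filters on its own.

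Third, selection is a matter of degree. With an assumed within-person SD of 12 mmHg, about 8% of non-responders also fail the average rule, and controls who improve under usual care are screened out as well.

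A reader might infer that the enrolled ALTA sample is known to be enriched for non-responders, and that the trial's BP control and PDC effects are therefore biased toward no effect. The documents do not support that. They give neither the time from exposure to screening nor a settled analysis set.

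**Conclusion.** The concern holds as a gap in the eligibility definition that allows selection on response. Following sections 6.3.3, 6.3.4 and 6.3.6 as written, months on ALTA can count toward eligibility and patients who improved can be excluded. Section 6.1.1 contradicts that procedure without resolving it.

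The size is zero with no exposure before screening, small if screening falls in the first one to three months, and substantial by 6 to 12 months (21–40% and 40–68% no longer qualifying, the complements of the table). These figures rest on assumed effects, the average-BP reading, and no diastolic or visit-to-visit variation. They show direction and growth with exposure and are not estimates for this trial.

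The reach is the relationship outcomes, the ALTA-versus-control comparison and objective 8. It extends to the main BP control and PDC analyses only if these use the 700 consented patients and not the EHR report.

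**What to change.** In the synopsis and section 5.3.2, end both look-backs the day before a single index date defined the same way for ALTA patients and controls. A workable choice is the date the patient was first identified as ALTA-eligible in the practice registry after the practice started ALTA, before any coaching. Separate anchors for the two groups would bring in a new asymmetry. Patients who cross over keep the date they already have. State that values after the index date do not affect eligibility, and put the date on the screening form. Recheck patients already screened from stored EHR dates. Reconcile sections 6.1.1, 6.3.4 and 6.3.6 on when patients are recruited, and state which patients form the analysis set for BP control and PDC.

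The cost is a short protocol change, one form field, one EHR re-extraction and some re-contact. The planned sample size and visits do not change. One limit remains: patients added late would still have no pre-ALTA survey.

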3.3 Introductory Statement

This document is a protocol for a human research study. The purpose of this protocol is to ensure that this study is to be conducted according to ICH GCP guidelines (CRF 21 Part 312), applicable government regulations and Institutional research policies and procedures.

2 – Background

2.1 Background/prevalence of research topic

Despite increasing awareness and treatment of hypertension (HTN) across all racial/ethnic groups, Latinos have the lowest blood pressure (BP) control rates in the US (Latino adults: 34% vs. 43% and 53% in non-Hispanic black and white adults). Among Latino adults in particular, rates of BP control are lower than among non-Hispanic black and white adults (35%, 43%, and 48%, respectively). Importantly, data from the NHLBI-sponsored Hispanic Community Health Study/Study of Latinos showed significant deficits in the treatment and control of HTN, with Latino men from Central American, South American and Dominican ancestry (Latino subgroups largely concentrated in the northeast US) experiencing the lowest rates of BP control (12%, 25% and 27%, respectively) compared to Mexican American men (31%). Similar patterns were seen in Latino women, with the poorest rates of BP control among women of Central American and Cuban descent (32% and 38%, respectively). Overall, these rates are considerably lower than rates of BP control among whites (48%).

These statistics may be explained by the disproportionately poorer adherence to antihypertensive medications among Latinos compared to blacks and whites. Despite the availability of numerous efficacious medications to manage HTN, 33-50% of hypertensive patients have uncontrolled HTN due to poor adherence to antihypertensive medications. The asymptomatic nature of HTN makes non-adherence a greater problem than in other chronic diseases, resulting in high costs due to non-adherence-related hospitalizations, repeat clinic visits, lost productivity, and increased morbidity and mortality. Multiple studies have documented disproportionately poorer medication adherence among Latinos compared to black and white patients.

3 – Rationale/Significance

